# 8.2 Efficacy Assessments

Tumor assessments will be performed by the investigators based on RECIST 1.1, which will also guide treatment decisions. All scans for tumor assessments performed during the study should be archived in accordance with the standard local practice. The scans must be accessible in the event of a Sponsor request to submit them for central review.

Tumor assessments will be carried out every 9 weeks (±3 days) after initiating study treatment, prior to initiation of each odd treatment cycle starting at Week 9, then every 6 weeks through the first year and then every 9 weeks, thereafter. CT/MRI scans of chest, abdomen, and pelvis and of other known sites of disease will be obtained at screening (within 28 days prior to Cycle 1 Day 1), at all tumor assessment time points, and as indicated clinically. Color photographs containing a millimeter scale must be taken of all skin lesions being used as target lesions. Historical standard of care scans that are performed with scanning parameters consistent with the requirements for this protocol within 28 days prior to dosing are acceptable. Subjects with squamous cell carcinoma of the head and neck must also have head and neck scans performed.

MRI may be used instead of CT for head, neck, abdomen, and pelvis; however, the chest must be assessed using CT. Chest disease may not be followed using chest x-ray. PET scanning should not be used, but PET/CT may be used if CT component is with contrast enhancement and of diagnostic quality.

A brain scan (CT with contrast or MRI pre- and post-gadolinium) must be performed at screening to assess potential CNS disease and/or metastases for patients with predilections to develop CNS metastases. For subjects with previously treated eligible brain metastases, a brain scan must be performed at all tumor assessment time points. For all subjects, a follow-up brain scan must be performed to confirm CR within 1 week of response confirmation, or if clinically indicated.

The tumor assessment schedule should not be affected by interruptions in study treatment.

Subjects taken off study treatment without disease progression will also undergo tumor assessments per the Study Calendar (Table 4) until disease progression is documented or another anticancer therapy is initiated.

The same method of assessment must be used at all time points as was used at screening. Throughout the study it is critical that the same imaging methodology be applied, and contrast be consistently provided unless IV contrast becomes medically contraindicated during the course of treatment or the dose of contrast needs to be adjusted based on the subject's health status. In order for SD to be considered the BOR, it must occur  $\geq$  5 weeks following the first dose of study drug.

The first radiological assessment of tumor response status will be performed at Week 9 (±3 days), unless there is clinical indication warranting earlier radiologic imaging. If imaging at Week 9 shows SD, treatment will be continued and tumor assessments will be conducted at the next regularly scheduled imaging time point, i.e., every 6 weeks through the first year, then every 9 weeks, thereafter. Responses (PR or CR) should be confirmed no less than 4 weeks after the initial response, but generally at the next scheduled tumor assessment time point.

If the time point tumor assessment is PD, treatment may be continued and tumor assessments be repeated at least 4 weeks later, but generally at the next scheduled tumor assessment time point in order to confirm PD. If repeat imaging shows a reduction in the tumor burden compared to the initial tumor assessment demonstrating PD, treatment may be continued as per treatment schedule. If repeat imaging confirms PD, subjects will be considered for discontinuation from study treatment. In determining the tumor time point response, investigators should consider all target lesions as well as non-target lesions and new lesions. The decision to continue study treatment after the first evidence of PD is at the investigator's discretion based on the clinical status of the subject. However, subjects may continue to receive study treatment in the setting of PD if they are deriving clinical benefit in the opinion of the investigator.

Subjects may continue receiving study treatment while waiting for confirmation of PD if they are clinically stable as defined by the following criteria:

- Absence of signs and symptoms (including worsening of laboratory values) indicating disease progression
- No decline in ECOG performance status
- Absence of rapid progression of disease
- Absence of progressive tumor at critical anatomical sites (e.g., cord compression) requiring urgent alternative medical intervention

If PD is confirmed and the subject is experiencing clinical benefit, the site may continue study treatment.

# 8.2.1 Objective Response Rate

ORR is defined as the proportion of subjects who have BOR of CR or PR as measured by RECIST 1.1 (see APPENDIX V).

ORR is measured from the start date of the treatment period until date of death from any cause. Subjects who are lost to follow-up and the subjects who are alive at the date of data cutoff will be censored at the date the subject was last known alive.

# 8.2.2 Disease Control Rate

DCR is defined as the proportion of subjects who have BOR of CR or PR or SD (duration of  $SD \ge 5$  weeks).

#### 8.2.3 Duration of Response

DOR is defined as the duration of CR or PR.

#### 8.2.4 Durable Stable Disease Rate

Durable SD rate is defined as the proportion of subjects whose BOR is SD and the duration of SD is  $\geq$  23 weeks.

#### 8.2.5 Clinical Benefit Rate

CBR is defined as the proportion of subjects who have BOR of CR or PR or durable SD (duration of SD  $\ge$  23 weeks).

#### 8.3 **Progression-Free Survival (PFS)**

PFS is defined as the time from the first study dose date to the date of first documentation of confirmed disease progression or death (whichever occurs first).

# 8.4 Overall Survival

OS is measured from the date of initiating study treatment to the date of death.

#### 8.5 Pharmacokinetics

Plasma concentrations of APR-246 will be measured in Cycle 1 and again in Cycle 3, at the timepoints provided in Table 5.

APR-246 plasma collection timepoints a	D1	D2	D3	D4
Prior to APR-246 infusion	×	×	×	×
At the end of APR-246 infusion	×		×	
1 hour after the end of APR-246 infusion	×		×	
3 hours after the end of APR-246 infusion	×			

**Table 5.** PK Blood Sampling Timepoints for APR-246 in Cycle 1 and Cycle 3

a A window of ±15 min applies to each time point.

The data will be evaluated using population pharmacokinetics (see section below).

#### 8.6 Electrocardiographic Assessment

 Table 6 describes the routine ECG requirements from screening through Cycle 4:

Time Point	ECG, number	Timing
Baseline/Screening	Triplicate	Must be within 28 days of C1D1
Cycle 1, Days 1-4	Triplicate	Pre-dose; Post dose (at the end of infusion; ± 10 min)
Cycles 2+, Day 1	Triplicate	Pre-dose

 Table 6. ECG Assessment Requirements

If repeated QTcF measurements show a stable QTcF < 450 msec, or if QTcF remains stable within the interval of 450 – 469 msec with no significant change at the EOI during several cycles of treatment, reducing the number of ECGs performed in the study may be discussed with the Medical Monitor.

If a subject starts treatment with another medication known to prolong QT interval at any time during the study therapy, an additional pre- and post-dose (6 hours after start of infusion,  $\pm$  30 min) ECG should be performed on the next treatment day.

Please consult Section 6.3.1 for additional requirements for proceeding with treatment with APR-246.

# 8.7 Correlative Studies

# Blood and serum biomarkers

Peripheral blood samples will be collected at specified time points for all enrolled subjects. Peripheral blood mononuclear cells (PBMCs) will be isolated and stored for future flow cytometry analyses. Serum samples will be stored for future cytokine analyses.

# Archived, formalin-fixed paraffin-embedded (FFPE) tissue

Optional archived FFPE tumor tissue samples will be collected from all subjects for potential assessment of mutations and other genetic alterations and/or proteins including PD-1/PD-L1 status and other relevant biomarkers (e.g., tumor infiltrating lymphocytes, T cell repertoire, ribonucleic acid [RNA] signature profiles) which may be important in the development and progression of cancer as well as for potential use in diagnostic development. Appropriate technology/methodologies will be used based on the amount of tumor tissue available.

#### Fresh tissue

For all tumor types, optional fresh tumor biopsies will be collected at baseline and on treatment to examine markers of target engagement, relevant pharmacodynamic biomarkers, and potential markers of response. Fresh biopsies should be limited to readily

accessible tumor lesions (e.g., skin, peripheral lymph nodes, liver metastases that can be readily accessed using CT guidance). Subjects should have the biopsy before administration of the first dose of study drug and at a time point 3 weeks after the first dose (if they have recovered adequately from the biopsy taken prior to starting therapy).

Instructions for the processing, storage, and shipping of samples will be provided in the Laboratory Manual.

# Pharmacokinetic-Pharmacodynamic Analyses:

Data from both safety lead-in and exploratory portions of the study will be used to explore PK/PD relationships for effects of APR-246 in combination with pembrolizumab on ORR, other efficacy-related parameters including PFS and OS, AEs/dose reductions, and Phase 2 blood and tumor biomarkers. Exploratory/graphical analyses will be conducted for PK/PD evaluations and may be followed by model-based analyses.

# 9.0 STATISTICS

# 9.1 Sample Size

In the safety lead-in portion of the study, up to 18 DLT-evaluable patients will be enrolled to determine the RP2D.

The dose expansion consists of 3 cohorts. The ORRs to pembrolizumab for the patients with the 3 types of cancer, who were R/R to previous chemotherapies, were 21.1% and 22,7% for urothelial cancer and gastric/GEJ adenocarcinoma, respectively. The ORR for patients with advanced NSCLC who have previously been treated with anti-PD-1/PD-L1 therapy is expected to be negligible (i.e. <= 20%). As such, the expected response rate to the combination therapy across indications is 20% to 30%. In order to increase the estimate precision, at least 20 evaluable patients will be included in each of the 3 cohorts.

Table 7 summarizes the 95% CI of response rates of 20% and 30% by the sample size. For example, if the sample size is 20 patients, at least 2 responders are needed to be over the lower boundary of 95% CI of 20% response rate.

**Table 7.** 2-sided 95% Confidence Interval for the ORR of 20% and 30% (20, 30 and 40sample sizes)

	95% CI for 20% ORR	95% CI for 30% ORR
N=20	(5.7%, 43.7%)	(11.9%, 54.3%)
N=30	(7.7 %, 38.6%)	(14.7 %, 49.4%)
N=40	(9.1 %, 35,6%)	(16.6 %, 46.5%)

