	The dose expansion consists of 3 cohorts. The ORRs to pembrolizumab for the patients with the 3 types of cancer, who were relapsed/refractory R/R to previous chemotherapies, were 21.1% and 22,7% for urothelial cancer and gastric/GEJ adenocarcinoma, respectively. The ORR for patients with advanced NSCLC who have previously been treated with anti-PD-1/PD-L1 therapy is expected to be negligible

(i.e. <= 20%). As such, the expected response rate to the combination therapy across indications is 20% to 30%. In order to increase the estimate precision, at least 20 evaluable patients will be included in each of the 3 cohorts.
Analysis Populations
Safety population: Subjects will be evaluable for safety if they receive at least one dose of APR-246. The safety population will be used to summarize exposure and safety parameters.
DLT-evaluable population: In the safety lead-in portion of the study, subjects who either experience a DLT during first the 3 weeks (Cycle 1) of the study treatment or receive $\geq$ 75% of scheduled Cycle 1 dose of APR-246 in combination with pembrolizumab and do not experience a DLT. Any individual subject who is not evaluable for DLT will be replaced by a new subject through additional subject enrollment.
Efficacy evaluable (EE) population: All subjects who complete at least one treatment cycle of APR-246 in combination with pembrolizumab and who have at least one post-treatment clinical response assessment. Subjects who fail to complete one treatment cycle will also be considered EE if they show clear evidence of clinically significant disease progression. The EE population will be the secondary analysis population for efficacy.
PK population: Subjects will be evaluable for PK if at least one post-dose sample for PK evaluation has been obtained.
PK/Pharmacodynamic population: All the subjects who receive at least 1 dose of study drug (APR-246 pembrolizumab) and have evaluable pharmacodynamic and concentration data.
Statistical analysis
All the statistical analysis will be detailed in the statistical analysis plan.

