### Table 1. APR-246 Dose Levels

Once the RP2D of APR-246 in combination with pembrolizumab has been determined, the expansion portion will begin in order to assess the anti-tumor activity of this combination in specific disease types. Up to 100 subjects will be enrolled in three cohorts of subjects with specific solid tumor malignancies as outlined in the schema.

Throughout the study, subjects may study continue treatment as long as toxicity remains acceptable and the subject has not withdrawn consent. Response and progressive disease (PD) will be assessed based on RECIST 1.1 response criteria (APPENDIX V) as outlined in the Study Calendar.

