# **5.0 SELECTION AND WITHDRAWAL OF SUBJECTS**

#### 5.1 Inclusion Criteria:

- 1. Signed informed consent form (ICF) and ability to comply with protocol requirements.
- 2. Known tumor TP53 mutation status from recent or archival sample.
- 3. Histologically and/or cytologically confirmed solid tumor malignancy:
  - a. Safety lead-in portion:
    - i. Patients with histologically and/or cytologically confirmed diagnosis of advanced non-CNS primary tumors that have progressed after first line treatment, who are intolerant to first line treatment, or who are unable to receive first line treatment, and for whom pembrolizumab, or pembrolizumab-based therapy, is considered appropriate in the opinion of the investigator. Primary CNS tumors are excluded. Patients with clinically stable, known metastatic tumors to the CNS are eligible. CNS radiography is not required in the absence of suspicion for clinical involvement.
  - b. Phase 2 Expansion portion:
    - i. Patients with histologically and/or cytologically confirmed diagnosis of advanced gastric or GEJ tumors that have progressed after first line treatment, who are intolerant to first line treatment, or who are unable to receive first line treatment. Patients with clinically stable, known metastatic tumors to the CNS are eligible with Medical Monitor approval. CNS radiography is not required in the absence of suspicion for clinical involvement. Prior treatment with anti-PD-1/anti-PD-L1 therapy is prohibited.
    - ii. Patients with histologically and/or cytologically confirmed diagnosis of advanced bladder/urothelial tumors that have progressed after first line treatment, or who are intolerant to first line treatment, or who are unable to receive first line treatment with cisplatin-based chemotherapy. Patients with clinically stable, known metastatic tumors to the CNS are eligible with Medical Monitor approval. CNS radiography is not required in the absence of suspicion for clinical involvement. Prior treatment with anti-PD-1/anti-PD-L1 therapy is prohibited is prohibited.
    - iii. Patients with histologically and/or cytologically confirmed diagnosis of advanced NSCLC previously treated with anti-PD-1 or anti-PD-L1 therapy. Patients with clinically stable, known metastatic tumors to the CNS are eligible with Medical Monitor approval. CNS radiography is not required in the absence of suspicion for clinical involvement.
- 4. Adequate organ function as defined by the following laboratory values:

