# 9.3 Data Summaries

Generally, all the continuous variables will be summarized using n (number of subjects with available data), mean, standard deviation (StDev), median, and range (minimum and maximum). Categorical data will be summarized by frequency and percentage. Time to event data will be analyzed using Kaplan-Meier method, and the number and percentage of events, or censored, the first quartile at 25%, median with 95% confidence, and third quartile at 75% of survival time will be presented. The survival rate at the 3, 6, 9, and 12 months, and then 2, 3 and 5 years will be presented. All the study data will be listed.

The following general study data, demographic, baseline characteristics and disease history will be summarized:

- Subject disposition
- Protocol deviation
- Demographics
- Cancer disease diagnosis and history
- Prior cancer treatments
- Medical history
- Prior/concomitant medications

Safety data including AEs, vital signs, laboratory data, ECG, physical exam, ad ECOG performance status will be summarized in the safety population. AEs will be coded using MedDRA and graded using NCI-CTCAE v5.0 severity grade.

The efficacy endpoints in the safety lead-in portion will be listed only. In the expansion phase, all the rates will be summarized with 95% exact CI (Clopper and Pearson) by cohorts. The time to event data will be analyzed using Kaplan-Meier method and the corresponding survival plots will be produced.

To assess any DDI between APR-246 and pembrolizumab, the primary PK parameters of APR-246 will be compared graphically and via descriptive statistics with historical data using the PK analysis set. If warranted, additional analyses may be performed. A popPK model for APR-246 will be developed. The model will be parameterized in terms of CL and Vd.

The effect of APR-246-pembrolizumab combination therapy on soluble, tissue, genetic and/or imaging biomarkers will be summarized using descriptive statistics using the PK/pharmacodynamic analysis set. PK/pharmacodynamic relationships will be explored graphically and may be investigated by model-based analyses.

Descriptive statistics/results from exploratory molecular analyses will be written and may include but are not limited to: TP53 variant allele frequency by next-generation sequencing (NGS), p53 immunohistochemistry, mutations in other genes by NGS, RNA expression.

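### Does the 2-of-20 responder example in Section 9.1 need replacing because it says nothing about activity beyond pembrolizumab?

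*Combined protocol and SAP*

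**What the plan says.** Section 9.1 starts from response rates to pembrolizumab in patients "who were R/R to previous chemotherapies, were 21.1% and 22,7% for urothelial cancer and gastric/GEJ adenocarcinoma, respectively". For lung cancer patients already treated with a checkpoint inhibitor it gives no point value: the rate after "anti-PD-1/PD-L1 therapy is expected to be negligible", with 20% as a ceiling. From these it takes an expected rate of 20% to 30% for the combination, and it sets the cohort minimum at 20 evaluable patients on grounds of precision. Table 7 shows 95% intervals for observed rates of 20% and 30% at N = 20, 30 and 40. The only responder count for objective response is the example that "at least 2 responders are needed to be over the lower boundary of 95% CI of 20% response rate".

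Section 4.1 gives the purpose of this part of the trial: "the expansion portion will begin in order to assess the anti-tumor activity of this combination in specific disease types". Section 9.3 gives the analysis: "In the expansion phase, all the rates will be summarized with 95% exact CI (Clopper and Pearson) by cohorts". Neither 9.1 nor 9.3 states a null rate, a success threshold or a formal comparison with the quoted pembrolizumab rates. Section 3.2 lists response rate as a secondary objective. The synopsis leaves analysis detail to the statistical analysis plan.

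**The concern.** Every patient receives both drugs and there is no control arm. A cohort's response rate therefore says little about what APR-246 adds unless it is set beside a rate for pembrolizumab alone. Section 9.1 has such rates to hand but uses them only to arrive at the 20% to 30% range. Its one worked count compares an observed rate with the lower limit of an interval around a hypothetical 4 of 20. A reader could take two responders of 20 as a bar for activity, although pembrolizumab alone would nearly always clear it.

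Two further points add to the unease. The quoted rates belong to patients relapsed or refractory to chemotherapy, while Section 5.1 (criterion 3b) is wider; the urothelial cohort, for example, also admits those "or who are intolerant to first line treatment, or who are unable to receive first line treatment with cisplatin-based chemotherapy". And a ceiling of 20% sits oddly with the word negligible, since 20% is also the lower end of the range expected for the combination. What would be at stake is over-reading a small single-arm cohort.

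**Working it through.** **Inputs.** From 9.1: N = 20, 30, 40; reference rates 21.1% and 22.7%; lung cancer ceiling 20%; expected combination rate 20% to 30%. From 9.3: Clopper-Pearson 95% intervals. Lung cancer references below 20% are assumptions, because the plan gives only the ceiling.

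**1. The plan's own figures.** For x responders of n, the lower limit is the 0.025 quantile of Beta(x, n − x + 1) and the upper limit is the 0.975 quantile of Beta(x + 1, n − x).

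| N | 20% observed | 30% observed |
|---|---|---|
| 20 | 4/20: 5.73% to 43.66% | 6/20: 11.89% to 54.28% |
| 30 | 6/30: 7.71% to 38.57% | 9/30: 14.73% to 49.40% |
| 40 | 8/40: 9.05% to 35.65% | 12/40: 16.56% to 46.53% |

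All six cells agree with Table 7. The example also holds: 1/20 = 5.0% < 5.7%, and 2/20 = 10.0% > 5.7%.

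**2. What 2 of 20 says about added activity.** P(X ≥ 2) = 1 − (1 − p)^20 − 20p(1 − p)^19.

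- p = 0.211: 1 − 0.0087 − 0.0467 = 0.945
- p = 0.227: 1 − 0.0058 − 0.0341 = 0.960
- p = 0.10 (assumed): 1 − 0.1216 − 0.2702 = 0.608

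The exact interval for 2/20 is 1.2% to 31.7%, which contains both quoted rates. The count carries almost no information about activity beyond pembrolizumab.

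**3. Counts at which the exact lower limit passes the reference**, with the binomial chance of reaching them at a true rate of 30%:

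| Reference | N = 20 | N = 30 | N = 40 |
|---|---|---|---|
| 21.1% urothelial | 9 (11%) | 12 (16%) | 15 (19%) |
| 22.7% gastric/GEJ | 9 (11%) | 13 (8%) | 15 (19%) |
| 20% lung, ceiling | 9 (11%) | 12 (16%) | 14 (30%) |
| 15% lung, assumed | 7 (39%) | 10 (41%) | 12 (56%) |
| 10% lung, assumed | 6 (58%) | 8 (72%) | 9 (89%) |
| 5% lung, assumed | 4 (89%) | 5 (97%) | 6 (99%) |

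Limits near the boundary: 8/20 gives 19.12% and 9/20 gives 23.06%; 12/30 gives 22.66% and 15/40 gives 22.73%. Against 22.7%, 12/30 misses by 0.04 points and 15/40 clears by 0.03.

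**4. Would the report change?** The planned output is the response rate and exact interval for each cohort. Both depend only on responders and patients, and no benchmark wording in 9.1 enters either. A reader who wants the comparison can read the reported lower limit against 21.1% or 22.7% directly.

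**The case for a change.** The strongest case for a change is that a reference fixed before data are seen cannot be chosen afterwards. The plan's own method and rates supply counts far more telling than 2 of 20, and the cost is a few sentences. Printing them would show openly that, in the urothelial and gastric/GEJ cohorts, a true 30% has only an 8% to 19% chance of putting the lower limit above the quoted rate. That arithmetic is right, and the observation that 9.1 never links the intervals to the rates stands.

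The remedy is less secure than the observation. It would commit the intervals to be read against rates that come from a narrower population than the one enrolled. For lung cancer it needs a reference that the plan does not give: taking the 20% ceiling produces 9 of 20, while assumed references of 5% to 15% produce 4 to 7. Counts of this kind, printed with a disclaimer that they are not a test, would tend to be used as one. The stated objective is the response rate of the combination, and nothing in the plan sets superiority over pembrolizumab as an aim. The synopsis also defers analysis detail to the statistical analysis plan, where a benchmark could be set if one were wanted.

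**Conclusion.** The concern does not call for a change. Section 9.1 contains no numerical error: Table 7 reproduces in all six cells, and the 2-of-20 sentence is a correct illustration of precision, which is the stated basis for the cohort size. It is a poor guide to added activity (passed 94.5% to 96.0% of the time at the quoted pembrolizumab rates), but the plan does not use it as one. The analysis is descriptive, on a secondary endpoint, and the same estimates and exact intervals would be reported either way. An analyst interpreting them would set them beside the quoted rates and mention the difference in population as a matter of course.

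The tension between negligible and at most 20% for lung cancer is loose wording. It enters no calculation beyond the general 20% to 30% range.

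This conclusion assumes that no go/no-go decision is tied to the 2-of-20 count; none appears in the plan. The counts for the urothelial and gastric/GEJ cohorts take 21.1% and 22.7% as fixed. Those for lung cancer depend on an assumed reference between 5% and 20%.
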